#### 12.1.1.1. Assessment of Adverse Events

Investigators will seek information on AEs at each subject contact. Subjects should be asked using a general, non-direct question if there has been any change in their general health. Direct questioning and examination should then be performed as appropriate.

Severity of the AE should be assessed according to the following criteria:

**Mild:** No interference with the subject's daily activities; no medical intervention/therapy required.

**Moderate:** Possible interference with the subject's daily activities; no or minimal medical intervention/therapy required.

**Severe:** Considerable interference with the subject's daily activities; medical intervention/therapy required.

Regardless of severity, some events may also meet regulatory serious criteria. Refer to definitions and reporting of serious adverse events (SAEs) in [Section 12.1.2](#).

An Investigator who is medically qualified must make the determination of relationship (related or not related) to the investigational product for each AE or SAE. When determining relationship to study medication, the Investigator will consider any investigational products that a subject could be exposed to in this clinical trial. The Investigator should decide whether there is a reasonable possibility that the study medication caused the event, taking into account the following: a) evidence b) science-based rationale c) medical and clinical judgment d)

mechanisms of action e) biologic plausibility f) confounding risk factors (i.e., medical history, concomitant medications) g) temporal relationship h) dechallenge/rechallenge and i) lack of alternative explanation.

- The event may be recorded as **Related** to investigational product if:
  - There is a plausible temporal relationship between the onset of the AE and administration of the study medication
  - The AE abates or resolves upon discontinuation of the study medication or dose reduction and, if applicable, reappears upon rechallenge
  - The AE cannot be readily explained by the subject's clinical state, intercurrent illness, or concomitant therapies
  - The AE follows a known pattern of response to the investigational product
- Reporting the event as **Not Related** to study medication may be considered if:
  - There is good evidence that the AE has an etiology other than the investigational product (e.g., pre-existing medical condition, underlying disease, intercurrent illness, or concomitant medication)
  - The AE has no plausible temporal relationship to administration of the investigational product (e.g., cancer diagnosed 2 days after first dose of study medication)

#### **12.1.1.2. Reporting Adverse Events**

AEs, whether spontaneously reported by the subject or noted by authorized study personnel, will be recorded in the subject's medical record and on the appropriate AE electronic case report form (eCRF). Each recorded AE will be described by its duration (represented in dates), affected eye(s) (if applicable), maximum severity of the AE, seriousness criteria, suspected relationship to the study medication, actions taken with the study medication and the study participation, outcome of the AE, and any other attributable causes of the AE.

Regardless of relationship to the clinical study, AEs that occur at any time after the subject has provided written informed consent until subject withdrawal or the scheduled exit visit, must be recorded. To improve the quality and precision of acquired AE data, Investigators should observe the following guidelines:

- Whenever possible, use recognized medical terms when recording. Do not use colloquialisms and/or abbreviations.
- If known, record the diagnosis (i.e., disease or syndrome) rather than component signs and symptoms and /or laboratory or test findings (e.g., record congestive heart failure rather than dyspnea, rales, and cyanosis, and enlarged heart on chest x-ray). However, other events that are considered unrelated to an encountered syndrome or disease should be recorded as individual AEs (e.g., if congestive heart failure and severe headache are observed at the same time and are clinically unrelated, each event should be recorded as an individual AE).

- If the diagnosis is not known, then record the leading component sign, symptom or test finding and describe the other clinically related findings in the narrative description of the case. A suspected diagnosis can be used and described as such (e.g., record suspected or probable myocardial infarction); this has to be updated in the clinical database once the diagnosis is confirmed.

AEs occurring secondary to other events (e.g., sequelae) should be identified by the primary cause. A primary AE, if clearly identifiable, generally represents the most accurate clinical term. If a primary AE is recorded, events occurring secondary to the primary event should be described in the narrative description of the case. For example:

The subject developed orthostatic hypotension and subsequently fainted and fell to the floor wherein she experienced a head trauma and neck pain.

The primary AE in this example is orthostatic hypotension. The fall, head trauma and neck pain should be described in the narrative description of the case.

- For intermittent events (e.g., intermittent headache), the event onset date should be recorded as the date the subject first started to experience the event and resolution date should reflect when the last occurrence resolved or stopped. Separate AEs for each event should not be recorded. For example, if a subject experienced headache on 14SEP2015 lasting for three hours, then subsequently experienced intermittent episodes of headache every day for approximately 3 hours until 21SEP2015, then the AE date of onset is 14SEP2015 and the resolution date is 21SEP2015.
- For intermittent events, record the maximum severity of the individual events. For example, if a subject complains of intermittent headaches for one week and the severity of each headache ranges from mild to moderate, then the severity would be moderate.
- For intermittent hospitalizations occurring for a primary AE (e.g., in a subject with multiple sclerosis, commonly known for its relapsing and remitting course, in some cases leading to multiple hospital confinements), the subsequent hospitalizations should be described in the narrative description of the case.
- If treatment was initiated, include the treatment and duration of the medication(s) in the eCRF.

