#### **12.1.3. Events of Special Interest**

The following are considered ESIs and should be reported on the appropriate eCRF with as much information as available within 24 hours of knowledge of the event:

- Pregnancy:
  - There are no controlled data with the investigational product in human pregnancy. It is required that females of childbearing potential use effective contraception during the study and recommended for 4 weeks for female subjects of childbearing potential and 12 weeks for male subjects capable of fathering children after the completion of the study. Any pregnancy occurring during study treatment should be reported and the subject will be discontinued from the study. The subject should be followed until the end of pregnancy or until the end of the study, whichever is longer.

- Medication administration errors
  - Study medication administration errors determined to be **significant** by the Investigator will be reported and evaluated as ESIs. Examples of study medication administration errors may include, but are not limited to: incorrect dose of study medication and administration of study medication from an incorrect kit. An AE does not necessarily need to have occurred to count as a study medication administration error. A medication administration error is an unintended failure in the process of treatment with a medicinal product that leads to, or has the potential to lead to harm of the subject.
- Macular edema (including cystoid macular edema):
  - Macular edema has been reported in some patients during the DE-117 clinical trials. Any cases of macular edema (including cystoid macular edema) should be reported in the ESI form in eCRF, or in case the EDC system is down, in the manual ESI form. Any cases of macular edema (including cystoid macular edema) will need to be followed until the event is determined to be resolved, irreversible, chronic, stable, the subject withdraws consent, or no further information can be reasonably obtained as per [Section 12.1.4](#).

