4.4.1.4. Events of Special Interest

Events of special interest (ESI) are pregnancy, clinically significant study medication administration error, and macular edema/cystoid macular edema.

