9.1. Adverse Events

AEs, SAEs, SARs, serious SARs, and significant AEs (AEs leading to study drug discontinuation and AEs leading to death) will be tabulated by type of AEs by treatment arm using actual treatment received for all AEs, ocular AEs, and non-ocular AEs separately.

Besides the overall AE summary, AEs, SAEs, SARs, serious SARs will be tabulated by SOC and preferred term for all AEs, ocular AEs, and non-ocular AEs separately. A subject who experienced multiple AEs within a SOC or preferred term will be counted only once for that SOC or preferred term. Non-serious AEs (including number of events) and ESIs will also be summarized by SOC and preferred term.

AEs, SAEs, SARs, serious SARs, ocular AEs, AEs leading to death, AEs leading to study drug discontinuation, non-TEAEs, and ESIs, if any, will be listed separately.

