9.1.1. Ocular Inflammation

Subjects who developed AEs during the study with one of the following preferred terms will be included in the ocular inflammation summary:

- Anterior chamber cell
- Anterior chamber flare
- Eye inflammation
- Iridocyclitis
- Iritis
- Uveitis

Ocular inflammation leading to study drug discontinuation, requiring steroid treatment, or requiring NSAIDs treatment will be summarized at the subject level by frequency and percentage separately.

Ocular inflammation start time (in terms of study day) and duration of the AE will be summarized at the eye level using mean, standard deviation, median, minimum, and maximum by study eye and fellow eye separately. To allow for the computation of simple descriptive statistics, only subjects who develop ocular inflammation during the study will be used for the ocular inflammation start time summary, and only subjects who develop these AEs during the study and later resolved will be used in the duration of AE analysis.

All ocular inflammation AEs will be provided in a listing.

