9.1.2. Macular Edema

Subjects who developed AEs during the study with one of the following preferred terms will be included in the macular edema summary:

- Macular edema
- Cystoid macular edema

Macular edema start time (in terms of study day) and duration of the AE will be summarized using mean, standard deviation, median, minimum, and maximum by study eye and fellow eye separately. To allow for the computation of simple descriptive statistics, only subjects who develop macular edema during the study will be used for the macular edema start time summary, and only subjects who develop these AEs during the study and later resolved will be used in the duration of AE analysis.

Change from baseline in BCVA at the onset of macular edema, when macular edema is resolved, and at the last visit will be summarized using mean, standard deviation, median, minimum, and maximum by study eye and fellow eye separately. Subjects with pseudophakic lens or phakic lens at baseline who developed macular edema during the study will be summarized by frequency and percentages separately.

The aforementioned summaries will be performed at the eye level. All macular edema AEs will be provided in a listing.

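### Adverse events secondary to another event go to the narrative only, while the SAP counts coded preferred terms, so listed or serious secondary events can be missing from their own rows and special summaries

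*Protocol*

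**What the plan says.** **Recording.** Protocol 12.1.1.2 sets the principle: "AEs occurring secondary to other events (e.g., sequelae) should be identified by the primary cause". Where a primary event has been recorded, its consequences go into free text: "If a primary AE is recorded, events occurring secondary to the primary event should be described in the narrative description of the case". The worked example is orthostatic hypotension followed by a faint and a fall. The hypotension is the AE, and "The fall, head trauma and neck pain should be described in the narrative description of the case". The section has no exception for a consequence that is itself serious, is an ESI, or is on one of the SAP's term lists.

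**Macular edema.** Protocol 12.1.3 adds a specific rule, with a 24-hour limit from knowledge of the event: "Any cases of macular edema (including cystoid macular edema) should be reported in the ESI form in eCRF". SAP 4.4.1.4 matches it: "Events of special interest (ESI) are pregnancy, clinically significant study medication administration error, and macular edema/cystoid macular edema".

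**Counting.** SAP 9.1 tabulates AEs by system organ class (SOC) and preferred term (PT), overall and separately for ocular and non-ocular events. On ESIs it says: "Non-serious AEs (including number of events) and ESIs will also be summarized by SOC and preferred term". The special summaries select by term. For inflammation, SAP 9.1.1 says: "Subjects who developed AEs during the study with one of the following preferred terms will be included in the ocular inflammation summary". For macular edema, SAP 9.1.2 says: "Subjects who developed AEs during the study with one of the following preferred terms will be included in the macular edema summary". SAP 9.1.3 does the same for cosmetic changes. SAP 4.4.1 takes treatment emergence from the AE's onset date and tabulates treatment-emergent AEs (TEAEs) only. SAP 4.4.1.1 to 4.4.1.3 take seriousness, affected eye and relationship from fields on the AE form.

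**The concern.** The two rules do not fit together. The protocol lets a consequence exist only as text attached to another event. The SAP can see an event only if it has its own record with a term, an onset date, an eye and a seriousness flag. A narrative-only event has none of these, so it cannot reach any table, however carefully the tables are programmed.

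The safety objective is a comparison of the two arms, and the SAP singles out ocular inflammation, macular edema and cosmetic changes for closer description. Inflammation has no ESI form behind it, so the AE record is the only source for the treatment, onset and duration figures in SAP 9.1.1. Sites may also differ in how readily they call an event secondary, so any undercount need not be uniform.

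**Working it through.** The plan gives no AE rates and no share of secondary events, so there is no figure of its own to reproduce. The check follows hypothetical chains of events through the recording and counting rules.

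1. **Inflammation secondary to an AE that is not on the SAP 9.1.1 list.** The primary event is recorded and the iritis or uveitis is narrative only. The subject stays in the any-AE count, but the inflammation has no PT row and is absent from SAP 9.1.1, including steroid or NSAID use, discontinuation, onset and duration.
2. **Cells or flare rolled into iritis.** Iritis is on the same list, so the subject stays in SAP 9.1.1. No loss from that summary.
3. **Macular edema following iritis or uveitis.** The inflammation is primary and is counted in SAP 9.1.1. The macular edema must go on the ESI form, and SAP 9.1 tabulates and lists ESIs. SAP 9.1.2, which reports onset, duration and visual acuity change at onset and resolution, is defined on AEs with the two listed terms. Protocol 12.1.1.2 read alone would not create that AE record. Neither document says that an ESI-form case must also be an AE record, or that the two sources are reconciled. The ESI table and the SAP 9.1.2 summary could therefore disagree.
4. **Primary and secondary events of different type.** SAP 4.4.1.2 classes an AE as ocular from the eye field on its own record. An ocular consequence of a non-ocular primary event, or the reverse, is missing from its side of the split unless the subject has another such AE.
5. **Primary event starting after consent but before first dose.** Protocol 12.1.1.2 records AEs from consent. Under SAP 4.4.1 this one is not treatment-emergent and appears only in the non-TEAE listing of SAP 9.1. A consequence that arises on treatment and is rolled into it enters no TEAE table.
6. **Secondary event that is itself serious.** The seriousness criteria in Protocol 12.1.2.1 include what an event led to, so the subject may stay in the serious count under the primary term. The serious consequence has no row of its own.

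**Scale.** Protocol 14.3.1 plans 200 adults per arm. One subject missing from a term lowers that arm's percentage by 1/200 = 0.5 percentage points; two lower it by 2/200 = 1.0 point.

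**The case against.** A reader might infer that macular edema, the drug risk the protocol names from earlier trials, drops out of the counts. The documents do not support that. The ESI rule covers every case with no exemption for secondary ones, and SAP 9.1 gives ESIs their own summary and listing. What remains is the missing link between the ESI form and SAP 9.1.2.

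A reader might also infer that all AE tables are understated. That is too broad. The primary event is recorded and coded, so the subject normally stays in the any-AE count, and in the ocular count too when both events are ocular. The loss is at the level of the specific term, organ class, split or special summary, apart from the pre-dose case.

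Further points carry weight:

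- Inflammation is lost from SAP 9.1.1 only when it follows an AE outside that list. The adult exclusions for a history of iritis or uveitis, and for macular edema or known risk factors for it, make such chains less likely.
- Attributing sequelae to a primary cause is a deliberate convention of the protocol, not an oversight.
- There is independent capture. SAP 9.3 tabulates cell and flare grades by visit and lists clinically significant worsening. SAP 9.4 gives a Month 3 shift for retina, macula and choroid. SAP 9.2 lists acuity changes of 0.2 logMAR or more.

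This capture is partial. Scheduled slit-lamp examinations after baseline are at Week 1, Week 6 and Month 3, so an episode that resolves in between can be missed. A cell or flare grade gives no diagnosis, treatment or duration. The ophthalmoscopy shift is normal or abnormal only.

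Finally, SAP 3.1 says enrollment had completed when the SAP was finalized, so a new recording rule cannot govern entries already made. That is correct, and it moves the weight of the remedy to steps before database lock.

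**Conclusion.** The mismatch is real. If sites follow Protocol 12.1.1.2 as written, a listed or serious secondary event can be missing from its PT or SOC row, from the ocular or non-ocular split when the primary event is of the other type, and from the special summaries. When the primary AE predates dosing, the secondary event enters no TEAE table. Ocular inflammation is the clearest exposure, because no second form backs it up. For macular edema the problem is limited to a possible disagreement between the ESI table and SAP 9.1.2.

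The size cannot be estimated from the documents. The 0.5 points per subject assumes an arm of 200 and a subject with no other record of the same term. The conclusion rests on two readings: that the worked example means no separate AE record, and that narratives are not coded, since neither document provides for it. Calling ocular inflammation a main risk of the drug would be an inference. The SAP gives it a dedicated summary, but the protocol does not make it an ESI. Efficacy analyses are not affected.

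**What to change.** 1. **Recording rule.** Add a sentence to Protocol 12.1.1.2: ESIs that are medical events, the preferred terms listed in SAP 9.1.1 to 9.1.3, and any event that is itself serious are recorded as separate AEs even when secondary to another AE.
2. **Narrative check.** Before database lock, have masked reviewers search existing narratives for those terms and for serious consequences, and query sites for a separate AE record where one is missing.
3. **Reconciliation.** Before lock, match macular edema cases on the ESI form to the AE dataset that feeds SAP 9.1.2, and resolve any differences.

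With enrollment already complete, steps 2 and 3 carry most of the value. SAP 9.1.3 already foresees a pre-lock look at AE data for additional cosmetic terms, so the narrative check could be done alongside it. The cost is one protocol sentence, a small amount of masked review work and slightly higher AE counts.

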### **12.1.2. Serious Adverse Events**

#### **12.1.2.1. Assessment of Serious Adverse Events**

An AE is considered serious if it fulfills one or more of the following criteria:

- Death (i.e., the AE caused or led to death).
- It was life threatening (i.e., immediately life-threatening).
- It required or prolonged inpatient hospitalization.
- It resulted in a persistent or significant disability/incapacity (i.e., the AE resulted in a substantial disruption of the subject's ability to carry out normal life functions).

- It resulted in a congenital anomaly/birth defect in the offspring of a study subject who was exposed to study therapy prior to conception or during pregnancy.
- It is a medically significant event(s), which may include “sight-threatening events,” that may not meet any of the above serious criteria but may jeopardize the subject or require medical or surgical intervention to prevent one of the outcomes listed above.

#### **12.1.2.2. Reporting Serious Adverse Events**

The SAE eCRF must be completed with as much information as is available within 24 hours of knowledge of the event.

To improve the quality and precision of acquired SAE data, Investigators should observe the following guidelines:

- Death: Death is an outcome of an event. The event that resulted in the death should be recorded and reported as the SAE.
- Hospitalizations for Surgical or Diagnostic Procedures: The illness leading to the surgical or diagnostic procedure should be recorded as the SAE, not the procedure itself. The procedure should be captured in the case narrative as part of the action taken in response to the illness.

Depending on the nature and seriousness of the AE, Santen may request additional documentation, for example, copies of the ophthalmic and medical records as well as results of laboratory tests. If the subject was hospitalized, a copy of the discharge summary may be requested.

#### **12.1.2.3. Expedited Reporting of Serious Adverse Events**

Santen (or designee) will provide the Principal Investigator with a reporting cover letter and a masked expedited safety report for expedited reporting of SAEs to the IRB or IEC. The Principal Investigator is responsible for receiving and reviewing expedited safety reports, submitting expedited safety reports to the IRB or IEC, and maintaining copies of expedited safety reports in the study records.

#### **12.1.3. Events of Special Interest**

The following are considered ESIs and should be reported on the appropriate eCRF with as much information as available within 24 hours of knowledge of the event:

- Pregnancy:
  - There are no controlled data with the investigational product in human pregnancy. It is required that females of childbearing potential use effective contraception during the study and recommended for 4 weeks for female subjects of childbearing potential and 12 weeks for male subjects capable of fathering children after the completion of the study. Any pregnancy occurring during study treatment should be reported and the subject will be discontinued from the study. The subject should be followed until the end of pregnancy or until the end of the study, whichever is longer.

- Medication administration errors
  - Study medication administration errors determined to be **significant** by the Investigator will be reported and evaluated as ESIs. Examples of study medication administration errors may include, but are not limited to: incorrect dose of study medication and administration of study medication from an incorrect kit. An AE does not necessarily need to have occurred to count as a study medication administration error. A medication administration error is an unintended failure in the process of treatment with a medicinal product that leads to, or has the potential to lead to harm of the subject.
- Macular edema (including cystoid macular edema):
  - Macular edema has been reported in some patients during the DE-117 clinical trials. Any cases of macular edema (including cystoid macular edema) should be reported in the ESI form in eCRF, or in case the EDC system is down, in the manual ESI form. Any cases of macular edema (including cystoid macular edema) will need to be followed until the event is determined to be resolved, irreversible, chronic, stable, the subject withdraws consent, or no further information can be reasonably obtained as per [Section 12.1.4](#).

